2.1 Hypothesis tested

The study intends to demonstrate that immediate abundant normal saline infusion after IVT is safe and effective in improving long-term functional outcomes in AIS patients treated with IVT.

2.2 Primary objective

The proportion of favorable functional outcomes (mRS 0-2) at 90 days.

2.3 Secondary objective

1. Secondary efficacy including mRS score at 30 and 90 days, Barthel index at 30 and 90 days, cerebrovascular events within 24 hours, 7 days and 90 days, NIHSS score at 7 days, END within 24 hours and laboratory examination at 24-48 hours.
2. Secondary safety including ejection fraction within 72 hours, death rate with any reasons within 90 days, intracranial hemorrhage and symptomatic intracranial hemorrhage within 7 days, blood pressure fluctuation within 24 hours and infarction edema volume at 24 hours.

3. Study Design

3.1 Trial plan

This is an assessor-blinded, randomized, controlled, two-arm (1:1 ratio) clinical trial registered at Clinicaltrials.gov (<http://www.clinicaltrials.gov>; unique identifier: NCT05993078) and has been approved by the Institutional Ethics Committee.

All patients within 4.5 h from the definite onset time are screened by the criteria of IVT recommended by European Stroke Organisation (ESO) guidelines on IVT for AIS at admission.[20] A cranial CT scan is conducted to exclude the ICH and large brain infarctions. The participants are

allocated to two arms: NS and control groups. In the NS group, the patients undergo an NS 2000 mL intravenous infusion swiftly after IVT at a speed of 200 mL/h. In the control group, the patients receive an NS 200-400ml after IVT. All the participants are subjected to CT at 24-h after IVT; if no brain hemorrhage occurs, antiplatelet drugs are used. In the event of brain hemorrhage, antiplatelet drugs are not used until the hemorrhage diminishes. Subsequent therapy is based on Chinese guidelines for diagnosis and treatment of acute ischemic stroke 2023.[21] All of the subjects should be treated in the hospital at least 7 days according to the guidelines for early management of stroke.

3.2 Selection criteria

3.2.1 Inclusion criteria

- (1) AIS;
- (2) Age 18-80 years;
- (3) Prestroke mRS≤1;
- (4) NIHSS score 0-25;
- (5) Onset-to-needle time≤4.5 h;
- (6) Sign the informed consent.

3.2.2 Exclusion criteria

- (1) Massive infarction, characterized by infarction area larger than 1/3 of the effected middle cerebral artery territory and/or the cerebellum territory presented in admitted computed tomography (CT) or magnetic resonance imaging (MRI);
- (2) Intention to undergo endovascular treatment;
- (3) History of heart failure or pre-IVT brain natriuretic peptide (BNP) $\geq 500\text{pg/ml}$ or having presentations or signs indicating heart failure;
- (4) Haemorrhage during IVT, including ICH, severe digestive haemorrhage and severe respiratory haemorrhage.

- (5) Allergy to thrombolysis drugs;
- (6) Intolerant to thrombolysis due to any reasons and had to terminate thrombolysis;
- (7) Arterial puncture at a non-compressible site within previous 7 days, major surgery within previous 14 days, sever trauma, gastrointestinal or urinary tract bleeding within previous 21 days;
- (8) Cerebral infarction or myocardial infarction within previous 3 months, previous ICH including parenchymal haemorrhage, intraventricular haemorrhage, subarachnoid haemorrhage, subdural/external haematoma, etc;
- (9) Severe brain trauma, intracranial or intraspinal surgery within previous 3 months or known malignant intracranial neoplasm, giant intracranial aneurysm or arteriovenous malformation;
- (10) Persistent systolic blood pressure ≥ 180 mmHg or diastolic blood pressure ≥ 100 mmHg;
- (11) Admitted blood glucose < 2.8 mmol/L or > 22.2 mmol/L;
- (12) Defect in coagulation, for example, current use of oral warfarin with an international normalised ratio > 1.7 , or prothrombin time > 15 s, or heparins during the last 48 hours, or use of direct thrombin inhibitors or direct factor Xa inhibitors during the last 48 hours or with an elevated activated partial thromboplastin time;
- (13) Known defect of platelet or clotting function, platelet count $< 100 \times 10^9$ /L;
- (14) Stroke mimics, such as seizure and hysteria;
- (15) Brain haemorrhage identified by CT or MRI;
- (16) Any terminal illness such that patients would not be expected to survive > 1 year;
- (17) Pregnant women or nursing mother;
- (18) Poor compliance, or inability to adhere to the trial protocol or follow-up
- (19) Participating in other clinical trials within previous 3 months.

3.2.3 Withdrawal criteria

- (1) Acute heart failure during interventions.
- (2) Hypertensive crisis during interventions.
- (3) Edema, such as severe cerebral edema, pulmonary edema, limb edema and water intoxication.
- (4) Other severe complications that should terminate the interventions immediately.
- (5) Stroke mimics.
- (6) Decide to undergo emergency endovascular treatment during interventions.
- (7) Refuse subsequent treatment and follow-up.

3.3 Follow-up time point

All included patients are followed-up at baseline, 24 hours, 7 days, 30 days and 90 days after randomization, respectively.

3.4 Randomization and masking

All patients are enrolled consecutively and randomized in 1:1 ratio to receive NS 2000ml or 200-400ml using a computer-generated randomization code. Sealed envelopes containing the allocation information (NS or control) will be labeled with sequential numbers prepared by an investigator who does not know screening of subjects. The researchers will enroll potential patients with a sequential number of opaque sealed envelopes, which will be opened only after obtaining informed consent. It is ensured that investigators are masked to the treatment allocation.

This is an open label trial, so we adopt a partial blinding strategy where the clinical assessors are blinded but the operators are not. That is, the neurological functional scores, imaging tests and laboratory assessments are assessed by investigators blinded to the intervention and grouping. The operators responsible for NS infusion to the patients are unblinded.

4. Trial Flow Chart

STUDY PROTOCOL									
	Enrollment	IVT ending	Interventions	Follow-up					
TIMEPOINTS	-1 h	0 h	0-10 h	24 h	48 h	Day 3	Day 7	Day 30	Day 90
ENROLLMENT									
Eligible Screen	X								
Informed Consent		X							
Allocation			X						
Termination Screen				X					
INTERVENTIONS									
NS 2000 mL				→					
NS 200-400 mL				→					
ASSESSMENT									
Baseline Data	X								
NIHSS score	X	X		X		X			
Cranial CT	X				X				
Blood Indices	X				—				
Laboratory examination	X				—				
Ultrasonic Cardiogram					—				
Cranial MRA/CTA					—				
Blood pressure					—				
mRS						X	X	X	

IVT: intravenous thrombolysis; NS: 0.9% normal saline; NIHSS: Institute of Health Stroke Scale; CT: computed tomography; MRA: magnetic resonance angiography; CTA: computed tomography angiography; mRS: modified Ranking scales.

5. Interventions

All patients within 4.5 hours from the definite onset time will be screened by the criteria of IVT recommended by European Stroke Organisation (ESO) guidelines.[20]

During thrombolysis, the patient or his certigiers will decide whether to participate in this trial. If they agree, an informed consent for NS-STAR trial will be signed, and allocation will proceed.

Participants will be allocated into two arms:

the NS group, undergoing immediate 2000 mL intravenous infusion of NS after IVT at a speed of 200 mL/h.

the control group, receiving 200-400ml of NS after IVT.

Subsequent therapy will follow the Chinese guidelines for the diagnosis and treatment of acute ischemic stroke 2023.[21] All subjects will be hospitalized for at least 7 days according to the guidelines for early stroke management.

6. Measurement

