Safety Outcomes	
 1. Ejection fraction within 72 hours. 2. Mortality within 90 days 3. Proportion of intracranial hemorrhage (ICH) and symptomatic ICH within 7 days. 4. Infarction volume at 24 hours after randomization. 5. Blood pressure fluctuation within 24 hours.
Trial Design	NS-STAR is a prospective, multicentre, randomised, open-label, blinded outcome reading, Phase II trial (PROBE design). Subjects included are randomly assigned into the NS group and the control group. Follow-up is performed at baseline, 24 hours, 7 days, 30 days and 90 days after randomization. The outcome assessors are blinded to the allocation

	assignment.
Trial Population	Patients with acute ischemic stroke treated by intravenous thrombolysis
Sample Size	240
Inclusion Criteria	
 1. Acute ischemic stroke. 2. Age 18-80 years. 3. Pre-stroke mRS≤1. 4. NIHSS score 0-25 5. Onset-to-needle time≤4.5 h. 6. Sign the informed consent.
Exclusion Criteria	
 1. Thrombolysis contraindication. 2. Allergy to alteplase. 3. intention to undergo emergency endovascular treatment. 4. Any terminal illness such that patients would not be expected to survive>1 year. 5. Poor compliance. 6. Participating in other clinical trials within previous 3 months.
Withdrawal Criteria	
 1. Acute heart failure during interventions. 2. Hypertensive crisis during interventions. 3. Edema, such as pulmonary edema, limb edema and water intoxication. 4. Other severe complications that should terminate the interventions immediately. 5. Stroke mimics. 6. Decide to undergo emergency endovascular treatment during interventions. 7. Refuse subsequent treatment and follow-up.
Trial Cycle	All included patients are followed-up at baseline, 24 hours, 7 days, 30 days and 90 days after randomization, respectively.
Treatment Regimens	Eligible patients are randomly (a ratio of 1:1) assigned into the NS group: undergoing immediate 2000 mL intravenous infusion of NS after intravenous thrombolysis at a speed of 200 mL/h, or the control group: receiving

	200-400ml of NS after intravenous thrombolysis. A standard therapy according to Chinese guidelines for diagnosis and treatment of acute ischemic stroke 2023 will be performed during the whole treatment period.

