11.1 Sample size

The sample-size is estimated according to previous trials with an expected between-group difference of 18 percentage points in favorable outcome (90-day mRS 0-2, 67.3% in the NS group and 49.3% in the control group).[4] Based on 0.8 power to detect a significant difference (2-sided $P=0.05$) and to compensate for nonadherence or dropout rate of 5%, we intend to enroll 120 patients per group (calculated by PASS, version 15.0, <https://passapp.io/>).

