11.2 Statistical analysis

The modified intention-to-treat analysis of efficacy outcomes and safety outcomes are performed on the full analysis set, which is composed of all patients who receive randomization independent of treatment and at least 1 efficacy evaluation after enrollment. The primary outcome is also performed with sensitivity analyses, including per-protocol analysis; imputation of missing primary outcome data under the scenarios of worst possible outcome, and best possible outcome. The χ^2 test is used in the unadjusted analysis. Modified Poisson regression model with robust error estimation is used in analysis of the primary outcome and other dichotomous end points, with adjustment for prespecified covariates

(age, sex, post-IVT NIHSS scores and onset-to-needle time). The relative risk (RR) with their 95% confidence interval (95%CI) is calculated in both unadjusted and adjusted analysis. Generalized linear models (GLMs) are conducted for analyse continuous end points, including NIHSS scores, Barthel scale, blood pressure, infarction volumes, ejection fraction at each follow-up time point. The full range score on mRS is analyzed by an ordinal logistic-regression model, and odds ratio (OR) with 95%CI are calculated. Cox regression model are used for analyzing the follow-up cerebrovascular events, presented with cumulative probability of events in Kaplan Meier cures. No interim analyses are performed in this study. The missing values of baseline variables in the covariate-adjusted analyses are replaced by mean values (continous variates) or mode (dichotomous variates) only if the number of them account for less than 10% in total.

A 2-sided P value <0.05 is considered statistical significance. Because multiple comparisons potentially cause type I error, findings for secondary outcome analyses should be interpreted as exploratory. SPSS software (version 26, IBM) and R software (version 4.1.0) are used for the statistical analyses.

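### Centre enters no planned analysis of this three-centre trial and the protocol does not say whether allocation is stratified by centre; adding it is a small, cheap gain in precision

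*Combined protocol and SAP*

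**What the plan says.** The Study Synopsis describes the trial as "prospective, multicentre, randomised, open-label, blinded outcome reading", and its Sites Number entry gives three centres.

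Section 3.4 (Randomization and masking) states that patients are "randomized in 1:1 ratio to receive NS 2000ml or 200-400ml using a computer-generated randomization code". On concealment it adds: "Sealed envelopes containing the allocation information (NS or control) will be labeled with sequential numbers". It mentions no block, stratification factor, minimization or per-centre envelope set.

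Section 11.2 (Statistical analysis) sets out the models:
- A plain χ² test for the unadjusted comparison.
- For binary endpoints, "Modified Poisson regression model with robust error estimation is used in analysis of the primary outcome and other dichotomous end points", adjusted for "age, sex, post-IVT NIHSS scores and onset-to-needle time".
- Generalized linear models for continuous endpoints, ordinal logistic regression for the full mRS, and Cox regression for cerebrovascular events.

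The covariate list is explicit and does not include centre. None of the models or the sensitivity analyses named in Section 11.2 uses centre.

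**The concern.** Three hospitals can differ in 90-day mRS 0-2 for reasons that age, sex, post-thrombolysis NIHSS and onset-to-needle time do not capture, such as local inpatient care and rehabilitation. If allocation ignores centre, each arm receives a chance mix of centres. For example, under simple randomization a 60-patient centre would split 24/36 or worse with probability 0.155. Differences between centres then pass into the treatment contrast.

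At stake is precision. The trial is sized at 80% power for a large difference and has little to spare. Centre is available without new data, assuming the site is recorded for each patient, as one would expect. The plan already adjusts for prognostic variables, so including centre follows its own logic.

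**Working it through.** **1. The plan's sample size.** Inputs from Section 11.1: "67.3% in the NS group and 49.3% in the control group", power 0.80, two-sided 0.05, 5% dropout. With the unpooled normal approximation:

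n = (1.960 + 0.842)² × (0.673×0.327 + 0.493×0.507) / 0.18² = 7.849 × 0.4700 / 0.0324 = 113.9, so 114 per group. Then 114/0.95 = 120.

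This reproduces the planned 120 per group, and nothing below changes it.

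**2. Chance shift from centre imbalance.** Assumed: centres of 120/60/60, with the largest centre having the lowest success rate. With centre shares w and centre rates p, the between-centre variance is σ² = Σ w(p − p̄)². If allocation ignores centre and the arms are equal, the shift in the risk difference has mean 0 and SD = 2σ/√240, where √240 = 15.49.

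| Centre rates (%) | p̄ (%) | σ² (points²) | σ (points) | SD of shift (points) |
|---|---|---|---|---|
| 55/60/65 | 58.75 | 17.19 | 4.15 | 0.54 |
| 50/60/70 | 57.50 | 68.75 | 8.29 | 1.07 |
| 45/60/75 | 56.25 | 154.69 | 12.44 | 1.61 |

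For 50/60/70, σ² = 0.5×7.5² + 0.25×2.5² + 0.25×12.5² = 68.75. In the last row, 1.96 × 1.61 = 3.2 points. Simulation with centres of 80/80/80, 120/60/60 and 160/40/40 gives SDs of 0.4-0.5, 0.7-1.1 and 1.1-1.6 points for spreads of 10, 20 and 30 points. The lower values there arise because the largest centre was given the middle rate: at 120/60/60 and a 20-point spread, σ² = 0.25×10² + 0.25×10² = 50 and SD = 2×7.07/15.49 = 0.91.

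**3. Efficiency against an unadjusted analysis.** The between-centre share of outcome variance is σ²/[p̄(1 − p̄)]:
- 10-point spread: 0.00172/0.2423 = 0.7%
- 20-point spread: 0.00688/0.2444 = 2.8%
- 30-point spread: 0.01547/0.2461 = 6.3%

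Two centre indicators cost roughly 2/240 = 0.8%, so at a 10-point spread gain and cost cancel. Simulated standard errors fall from 6.34 to 6.27 points at 50/60/70, where (6.34/6.27)² = 1.022, and from 6.36 to 6.17 at 45/60/75, where (6.36/6.17)² = 1.063. The gain is therefore about 0%, 2-3% and 6%. With no centre effect, simulation shows a loss of about 0.5%, up to about 1% with other centre sizes.

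**4. Power for 18 points.** With Φ(18/SE − 1.96), SE 6.36 gives Φ(0.870) = 0.81 and SE 6.17 gives Φ(0.957) = 0.83. At the 20-point spread, power moves from 0.810 to 0.819. A separate simulation (100,000 trials per scenario, allocation ignoring centre) compared the χ² test with the centre-stratified Cochran-Mantel-Haenszel (CMH) test, which stands in for a centre-adjusted model:

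| Spread (points) | 80/80/80: χ² | 80/80/80: CMH | 120/60/60: χ² | 120/60/60: CMH |
|---|---|---|---|---|
| 0 | 0.8136 | 0.8069 | 0.8152 | 0.8091 |
| 10 | 0.8135 | 0.8105 | 0.8128 | 0.8080 |
| 20 | 0.8170 | 0.8217 | 0.8155 | 0.8186 |
| 30 | 0.8137 | 0.8325 | 0.8157 | 0.8287 |

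The largest gain is 1.9 points and the largest loss 0.7. Stratifying the allocation as well gives 0.8356 for CMH at 80/80/80 and a 30-point spread.

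**5. Type I error.** With allocation ignoring centre, the χ² test rejects a true null in 0.045-0.047 of trials and CMH in 0.049-0.051, whatever the centre spread. If allocation is stratified by centre and the analysis ignores it, the χ² rate falls from 0.0457 (no centre effect) to 0.0392 (30-point spread, 80/80/80); CMH gives 0.0516.

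**The case against.** The strongest reply is that this is an optional efficiency gain and not an error. Under unstratified allocation, chance centre imbalance is already reflected in the ordinary standard error, so the planned test and interval are valid. That stands.

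Three stronger readings are tempting, and the documents do not support them.
- A reader might infer that the plan rules out blocking or stratification. Section 3.4 is silent on both; separate site lists may exist and simply not be described.
- A reader might infer that the primary estimate is biased. The shift has mean zero, and type I error is not inflated.
- A reader might take 6% as the gain over the planned adjusted model. The comparator above is an unadjusted analysis. Centre differences that act through the four covariates are already partly absorbed. The gain over the four-covariate model has not been computed and may be smaller.

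It is also fair to say that the centre spreads are assumptions. Shared selection criteria, a common thrombolysis guideline and a common treatment guideline (Sections 3.1, 3.2 and 5) argue for some homogeneity, and a 30-point spread is the top of the range shown. Finally, adjustment is not quite free: it loses a little if centre does not matter, and it changes what the ordinal odds ratio estimates.

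What remains is that Section 11.2 fixes a covariate list without centre in a three-centre trial, and adding centre has a small, bounded cost.

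**Conclusion.** The point holds as a minor improvement. Centre is absent from every planned analysis, and its role in allocation is unstated. With centres of 120/60/60, leaving it out allows a chance shift with an SD of about 0.5 to 1.6 points for spreads of 10 to 30 points, against an "expected between-group difference of 18 percentage points in favorable outcome". Compared with an unadjusted analysis, adjusting for centre is worth between nothing and about 6% in efficiency. These sizes rest on assumed centre sizes and rates. The case for including centre does not depend on how the silence in Section 3.4 is resolved: if allocation ignored centre, adjustment removes some noise; if it was stratified by centre, an analysis that ignores centre is mildly conservative.

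**What to change.** In Section 11.2, before outcome data are analysed, add centre (three levels, fixed effect) to the covariates of the modified Poisson, ordinal logistic and generalized linear models. Add it to the Cox model as a covariate or as a stratum.

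In Section 3.4, state whether the code is blocked or stratified by centre and how the numbered envelopes are divided among the three hospitals. For any envelopes not yet prepared, generate the list in permuted blocks of varying size within each centre.

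The cost is 2 degrees of freedom, up to about 0.7 points of power if centre does not matter, and an ordinal odds ratio that becomes conditional on centre and should be labelled so. The sample size does not change. No new data are needed if the site is recorded for each patient.

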6.1 Haematological examination and laboratory assessment

Baseline blood samples are obtained before IVT administration. The blood indices comprise blood routine, creatinine, urea, BNP, electrolyte and coagulation function. The blood routine is reassessed at 24-48 hours after randomization. Peripheral blood biomarkers that can reflect brain injury, including S100- β , brain derived neurotrophic factor (BDNF) and myeloperoxidase (MPO) are assessed before IVT administration and at 24-48 hours after randomization.

6.2 Imaging tests

Cranial CT scans are performed before IVT and 24 hours after randomization. The infarction area is confirmed using CT maps and the infarction volume is calculated by 3D-Slicer (Version 4.6.2, <https://www.slicer.org/>). Magnetic resonance angiography (MRA), CT angiography (CTA), or carotid artery ultrasound are used to evaluate cranial vessels.

6.3 Clinical observation

National Institutes of Health Stroke Scale (NIHSS) is commonly used to evaluate neurological deficits in patients with AIS and includes 15 items in 11 fields of different neurological statuses. The NIHSS is scored at admission, at the end of IVT, 24-h and 7-day after randomization during hospitalization.

END indicates an increase of ≥ 2 or ≥ 4 in the NIHSS score within 24 h after IVT, and the deterioration is not caused by ICH, which is confirmed by cranial CT.

Modified Rankin Scale (mRS) reflects disability at follow-up time, which consists of 7 disability levels, ranging from 0 (no symptoms) to 5 (severe disability), and 6 (death). We intend to assess the mRS on days 7, 30, and 90 after randomization.

Barthel index (BI) is a standardized tool used to evaluate a person's ability to perform basic activities of daily living independently at follow-up time, and consists of 10 items, ranging from 0 (total dependence) to 100 (complete independence). We intend to assess the BI on days 30 and 90 after randomization.

The ejection fraction is assessed by ultrasonic cardiogram within 72 hours after randomization.

Blood pressure, including systolic blood pressure (SBP) and diastolic blood pressure (DBP), is monitored from IVT initiation every 5 min for 2 h and then continuously assessed every 30 min for 6 h and every hour for 16 h. The 24-hour blood pressures are recorded (before IVT, after IVT, 10 hours, 12 hours and 24 hours after randomization).

7. Outcomes

7.1 Efficacy outcomes

7.1.1 Primary outcomes

Primary efficacy is independence at 90 days, as scored using the mRS, and dichotomized as a favorable (score 0-2) or an unfavorable outcome (score 2-6), following the Cochrane analysis of thrombolysis in stroke. The proportion of patients in each arm with favorable outcomes is compared at 90 days.

7.1.2 Secondary outcomes

(1) Proportion of patients with END (Δ NIHSS ≥ 2 and Δ NIHSS ≥ 4) at 24 hours after randomization.

Δ NIHSS indicates 24-hour NIHSS score minus post-IVT NIHSS score.

(2) Proportion of patients with cerebrovascular events within 1 day, 7 days and 90 days after randomization. Cerebrovascular events included progressive stroke (NIHSS deterioration ≥ 2 scores),

transient ischemic attack or new ischemic lesions confirmed by imaging.

(3) NIHSS scores at 7 days.

(4) Proportion of patients with mRS 0-2 at 30 days.

(5) mRS distribution at 30 days and 90 days.

(6) BI scores at 30 days and 90 days.

(7) Proportion of the patients with BI 60-100 at 30 days and 90 days.

(8) Peripheral blood inflammatory indices, including neutrophil-to-lymphocyte ratio (NLR), platelet-to-lymphocyte (PLR), lymphocyte-to-monocyte (LMR) and (platelet \times neutrophil)/lymphocyte (SII) at 24-48 hours after randomization.

(9) Laboratory examinations (S100- β , BDNF, and MPO) at 24-48 hours after randomization.

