It is well acknowledged that intravenous thrombolysis (IVT) is a safe and effective strategy for treating acute ischemic stroke (AIS) within 4.5 h in clinical settings.[1, 2] However, only approximately 30% of patients achieve long-term independence (modified Ranking scales 0-1).[3] A plethora of factors may influence the effectiveness of IVT, including age, comorbid diseases, stroke subtypes, infarct size and onset-to-needle time.[3, 4] Ultimately, all these factors can be attributed to reperfusion and the penumbra.[5] Therefore, the further elevation of the reperfusion rate and expansion of the ischemic penumbra after IVT are emerging challenges. A simple approach is to increase cerebral blood flow (CBF), which can reopen occluded vessels and rescue ischemic neurons after AIS. Intravenous administration of 0.9% normal saline (NS) is an easy-to-use strategy commonly used to expand volume.[6, 7] The benefit of NS infusion on stroke outcomes is not a concern, but for reperfusion therapies such as IVT, it seems to be practicable.

Investigations on volume expanders and hemodilution date back to the 1960s.[8] Since then, accumulating evidence has indicated that volume expansion can improve the collateral circulation status, reduce blood viscosity, and alleviate brain dysfunction.[9-12] Considering rescuing the ischemic penumbra, the early use of hemodilution, especially within 6 h after AIS onset, is inevitable to exert its powerful functions.[13] The no-reflow phenomenon and unexpected re-occlusion may be responsible for poor outcomes and early neurological deterioration (END) after IVT.[14] In theory, the early use of hemodilution after IVT can increase distal arterial perfusion and reduce the re-occlusion rate by increasing CBF. In addition, the prevalence of dehydration accounts for approximately 48%-53% of patients with stroke, in whom immediate fluid intake might improve their short- and long-term prognoses, especially in people undergoing thrombolysis.[15-19] Therefore, we hypothesized that immediate hemodilution after IVT may increase the reperfusion rate, reduce the re-occlusion rate, and improve prognosis.

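### S100-beta, BDNF, MPO and SII are compared between arms after a treatment meant to dilute the blood, with no planned check or correction for dilution

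*Combined protocol and SAP*

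**What the plan says.** - **Purpose.** Section 1 hypothesises that "immediate hemodilution after IVT may increase the reperfusion rate" and argues: "In theory, the early use of hemodilution after IVT can increase distal arterial perfusion".
- **Volumes.** Section 3.1: in the NS arm "the patients undergo an NS 2000 mL intravenous infusion swiftly after IVT at a speed of 200 mL/h"; in the control arm "the patients receive an NS 200-400ml after IVT".
- **Outcomes.** Section 7.1.2, item 8, lists NLR, PLR, LMR and SII, the last being platelets times neutrophils over lymphocytes: "neutrophil)/lymphocyte (SII) at 24-48 hours after randomization". Item 9 adds S100-beta with "BDNF, and MPO) at 24-48 hours after randomization". Section 6.1 describes the three proteins as markers of brain injury and has them measured before IVT as well.
- **Blood count.** Section 6.1: "The blood routine is reassessed at 24-48 hours after randomization". It is also part of the baseline sample. Haemoglobin and haematocrit are not named.
- **Analysis.** Section 11.2: "Generalized linear models (GLMs) are conducted for analyse continuous end points". The endpoints it then lists are NIHSS, Barthel, blood pressure, infarct volume and ejection fraction, with no mention of the proteins or SII. The prespecified covariates are age, sex, post-IVT NIHSS and onset-to-needle time. No dilution index, plasma-volume adjustment or baseline marker value appears. Secondary findings are to be read as exploratory.
- **A conflict.** Section 9.2 gives the 24-48 h markers as S100-beta, MBP and GFAP. Sections 6.1 and 7.1.2 give S100-beta, BDNF and MPO.

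**The concern.** A blood concentration is an amount divided by a volume, and this treatment is chosen to change the volume. The difference is caused by allocation, so randomisation does not balance it and blinded laboratory assessment does not remove it. Lower S100-beta, MPO or SII in the NS arm would naturally be read as less injury or inflammation, when some or all of it could be residual saline. For BDNF the documents state no direction of benefit; dilution shifts that comparison too, whichever way it is read.

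At stake is the interpretation of items 8 and 9 of the secondary outcomes. The plan also leaves unused a simple check on its own mechanism, because no outcome shows whether the NS arm's blood was more dilute at sampling.

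**Working it through.** **The plan's own figure.** No figure is given for the biomarkers, so the sample size is reproduced only to fix the number per arm. With 67.3% against 49.3%, two-sided alpha 0.05, power 0.80 and unpooled variance: n = (1.960 + 0.842)² × (0.673×0.327 + 0.493×0.507) / 0.18² = 113.9, so 114. Then 114/0.95 = 120, as section 11.1 states. I use 114 per arm below.

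**Timing.** 2000 mL at 200 mL/h takes 10 h. Counting the infusion from about randomization, samples at 24-48 h fall 14-38 h after it ends.

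**Which indices are affected.** Let dilution multiply every count by f.
- NLR: fN/fL = N/L. PLR and LMR cancel in the same way.
- SII: (fP)(fN)/(fL) = f × PN/L, so one factor f remains.
- S100-beta, BDNF and MPO: each is multiplied by its own dilution factor.

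**Size of the shift.** The documents do not give the share of saline still intravascular at sampling. Assumptions: retention r is equal in both arms and runs from 0 to 25%; volume V is 3000 mL plasma for the proteins and 5000 mL blood for the counts; control volume C is 400 or 200 mL.

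NS/control ratio = (1 + rC/V) / (1 + 2000r/V)

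Example, proteins, r = 0.25, C = 200: (1 + 50/3000)/(1 + 500/3000) = 1.0167/1.1667 = 0.871, or 12.9% lower.

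**False-positive rate.** Two-sided normal test at 0.05 on the log scale, no biological effect. The log scale and log-SDs of 0.5 and 0.8 are assumptions. SE = SD × √(2/114), which is 0.066 or 0.106. With δ = |ln ratio|/SE, rate = Φ(δ − 1.96) + Φ(−δ − 1.96). For the example, δ = 0.1376/0.0662 = 2.08 and the rate is 55%.

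| Retention | Proteins lower by | Rate, SD 0.5 | Rate, SD 0.8 | SII lower by | Rate, SD 0.5 | Rate, SD 0.8 |
|---|---|---|---|---|---|---|
| 0% | 0% | 5% | 5% | 0% | 5% | 5% |
| 5% | 2.6-2.9% | 6.8-7.3% | 5.7-5.9% | 1.6-1.8% | 5.7-5.8% | 5.3% |
| 10% | 5.0-5.6% | 12-14% | 7.7-8.5% | 3.1-3.5% | 7.6-8.3% | 6.0-6.3% |
| 25% | 11.4-12.9% | 45-55% | 21-25% | 7.3-8.2% | 21-25% | 11-13% |

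Within each cell the first figure is for 400 mL in control and the second for 200 mL.

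**The case against.** The strongest objection is that the infusion ends 14-38 h before sampling, so little or no saline may remain. That stands: nothing in the documents fixes retention, and at 5% the inflation is trivial. A reader might take the 45-55% rates as the expected error. The documents do not support that, because those rates need 500 mL still circulating in the NS arm, equal fractional retention in both arms and a log-SD of 0.5.

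Other points that stand:
- A reader might infer that the plan prescribes analysis of raw values. It does not say so; it gives no scale or model for these markers. What can be said is that no correction is planned.
- A reader might infer that any biomarker finding would be indistinguishable from dilution. That goes too far. On these assumptions dilution explains at most about 13%, and NLR, PLR and LMR are immune to it.
- A reader might assume haemoglobin and haematocrit are already captured. A blood routine would normally contain them, but the documents do not name them.
- The correction is itself fallible. A marker that is released and cleared quickly can return to its equilibrium concentration while volume is still expanded, and rescaling would then overcorrect it upward in the NS arm. The sample type (plasma or serum) is also not stated.

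The exploratory label answers less than it seems to. Section 11.2 ties it to multiplicity, which is a different problem from a shift in measurement caused by the treatment.

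**Conclusion.** The concern holds as a gap in the plan: four secondary efficacy measures depend on concentration, the intervention is intended to dilute, and there is neither a check nor a correction. The direction (lower in the NS arm) and the SII algebra are secure. The size is not known and may be nil: 0-13% for the proteins and 0-8% for SII over 0-25% retention. The error rates in the table depend on the assumed volumes, equal retention, log scale and SDs. That uncertainty is a reason to measure dilution; it does not show that the biomarker results will be wrong. The mRS primary outcome and the sample size are not affected. This is an inexpensive improvement confined to exploratory outcomes.

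**What to change.** Before anything else, reconcile section 9.2 (S100-beta, MBP, GFAP) with sections 6.1 and 7.1.2 (S100-beta, BDNF, MPO), so that it is clear which markers are measured. Then add to section 11.2:

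1. Change in haematocrit and haemoglobin from baseline to 24-48 h, by arm, as an exploratory outcome, after confirming that the CRF captures both at both times.
2. The uncorrected comparison of S100-beta, BDNF, MPO and SII, with its model and scale stated, plus a prespecified dilution-corrected sensitivity analysis. For SII, multiply the 24-48 h value by baseline haemoglobin over 24-48 h haemoglobin. For the proteins, multiply by the plasma-volume ratio from the Dill-Costill formula, (Hb₁/Hb₂) × (1 − Hct₂)/(1 − Hct₁), where 1 is baseline and 2 is 24-48 h. State the sample type. Flag patients with major bleeding or transfusion before the second sample, in whom the correction fails.
3. A rule that a biomarker effect is claimed only if it holds in both analyses.

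The cost is SAP wording and a few lines of code, using blood already drawn at both times, provided the CRF check succeeds. No visit, sample or sample-size change follows. The downsides are slightly more variance from haemoglobin measurement error and possible overcorrection of proteins with fast turnover, which is why the correction belongs in a sensitivity analysis.
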